5.1.4.3.2 Multiple imputation sensitivity analyses steps

The following steps are followed in order to create the structure of the analysis dataset where missing values and appropriate variables could be imputed.

- Obtain subject id, treatment group, stratification factor, sex, race group, age group, BMI group (subjid trt01pn mmstratn sexn race agemedn bmimedn) from ADBS, ADSL.
- Obtain number of prior migraine prophylactic treatment failed, baseline disease duration group (prophfln durmedn) from ADBS.
- Obtain avisitn paramcd param aval avalc base chg dtype from ADATTACK
- Perform minor data manipulation, as required, to reinstate the missing data, eg if dtype="LOCF" then aval=,, avalc="" " and chg=.

- Ensure the baseline values are included in the chg variables before data transformation, eg if avisitn=2000 is baseline then chg=base;
- Transpose all the data so you have one observation per subject and each visit becomes a variable within its own right, eg rows where avisitn=2004, 2008, 2012 etc become the column week4, week8, week 12 etc.
- Impute the missing data for MAR according to the methods in next steps

MAR multiple imputations steps:

Note that the some variable has missing values and there is a mix of categorical and continuous variables in the modelling of the missing data. Therefore, fully conditional specification (FCS) methods are employed within proc mi to impute the missing data.

- FCS logistic is used for dichotomous variables (mmstratn sexn agemedn bmimedn prophgrp durmedn); discrim is used for categorical variables with more than 2 categories (race); regpmm is used for continuous variables (wk0, wk4, wk8,... wk52).
- wk4, wk8 , ... and wk52 represent the chg variable for each of the visits respectively, and wk0 is baseline.

MAR modeling step:

- For the primary endpoint, first, define 50% Responders based on imputed MMD data under the assumption of MAR. Then, use the same method as for primary variable - the stratified CMH test to get estimates for numbers of responders in each treatment group and odds ratio at week 52 for each dataset.
- For change from baseline in MMD it is used a linear mixed effects model on imputing data under the assumption of MAR. There is no gaps in imputed data, therefore, all the data is available to analyze and can use a fixed effects model looking only at the avisitn=2052/week52 data.

MAR combining step:

- The output dataset with the treatment LS means (LSMEANS) and the treatment differences (DIFF) are then sorted, manipulated and read into proc mianalyze to combine the individual sets of imputed results into one set of overall results, see all steps SAS codes in TFLs document.

5.2 AEs coding/grading

Adverse events are coded using the Medical dictionary for regulatory activities (MedDRA) terminology. Adverse event severity is graded as shown below:

- mild: usually transient in nature and generally not interfering with normal activities
- moderate: sufficiently discomforting to interfere with normal activities
- severe: prevents normal activities

5.3 Laboratory parameters derivations

NA.

5.4 Rule of exclusion criteria of analysis sets

The protocol deviations during screening, baseline and treatment periods are defined below ([Table 5-3](#)). The deviation ID, deviation code and it's corresponding text description are explained in [Table 5-3](#). Subjects exclusion based on protocol deviations and non- protocol deviations criteria are in [Table 5-4](#).

Table 5-3 Deviation Codes Description

Deviation code	Text description	Deviation ID
1	SELECTION CRITERIA NOT MET	INCLXX ; EXCLXX
2	PATIENT NOT WITHDRAWN AS PER PROTOCOL	WITHXX
3	PROHIBITED CONCOMITANT MEDICATION	COMDXX
4	TREATMENT DEVIATION	TRTXX
998	OTHER	OTHXX

Table 5-4 Patient classification

Analysis Set	PD ID that cause subjects to be excluded	Non-PD criteria that cause subjects to be excluded
FAS	NA	Not randomized
SAF	NA	Not randomized; No study drug taken

5.5 Statistical models

5.5.1 Primary analysis

The null hypothesis stating that the odds ratio between the two treatment arms less than or equal to 1 will be tested against the one-sided alternative.

$H_0: \theta_1 \leq 1$ vs $H_1: \theta_1 > 1$

where θ_1 is the odds ratio of AMG334 over standard of care oral prophylactics.

After the missing data are imputed as non-response a Cochran-Mantel-Haenszel (CMH) test stratified by prior treatment failure=1 versus prior treatment failures=2 will be used under a significance level of 0.025, one-sided (0.05, two-sided) to evaluate the association between the 50% responder rate at month 12 and the treatment. The estimated common odds ratio, 95% confidence intervals and two-sided p-values will be reported.

Additionally, the estimated common relative risk and risk difference with their asymptotic (Wald) confidence limits will be provided.

The test can be implemented using SAS, PROC FREQ with options CMH, RELRISK, RISKDIFF under TABLE statement.

5.5.2 Secondary analysis

Follow same instructions as [Section 5.5.1](#) for secondary analysis using CMH test.

Linear mixed models using repeated measurements:

The secondary endpoint of the study cumulative average change from baseline on MMD will be tested for AMG334 compared to standard of care oral prophylactics, respectively.

- Null Hypothesis: In subject with episodic migraine, the AMG334 treatment group is the same as SoC, in terms of the reduction from baseline in cumulative mean monthly migraine days in month 12
- Alternative Hypothesis : In subject with episodic migraine, the AMG334 treatment group is different as SoC, in terms of the reduction from baseline in cumulative mean monthly migraine days in month 12

It will be analyzed using a linear mixed effects repeated measures model with treatment group, baseline value, stratification factor, scheduled visit, and the interaction of treatment group with scheduled visit. In repeated statement, an unstructured covariance matrix will be used.

The test can be implemented using SAS, PROC MIXED procedure.

5.6 Important derivations

- Subject-level End of Study (EOS) Date

The end of study (EOS) date for each subject is defined as the last date on which the subject participated in the study. The date will be recorded on the study disposition eCRF page.

- Duration of exposure of study treatment

For AMG334 calculation of exposure, dose date refers to receiving dose > 0 , but can include partial doses. The duration of exposure for AMG334 is computed as of last injection of study drug + 27 days - date of first injection of study drug +1.

For oral prophylactics arm calculation of exposure, dose date refers to receiving dose > 0 . The duration of exposure for initially assigned treatment is computed as last dose date - First Dose Date + 1.

- Compliance with the eDiary

The protocol requirement is 80% compliance in 28 days. That means a minimum 23 diaries must be completed within 28 days. Compliance to eDiary at each month is calculated as

- (Number of eDiary entered in baseline period or between IP doses/28days)*100% if the number of actual days in Baseline period or between IP doses interval is ≤ 28 days
 - (Number of eDiary entered in baseline period or between IP doses/ number of actual days in Baseline period or between IP doses interval)*100% if the number of actual days in Baseline period or between IP doses interval is > 28 days
 - eDiary Device Assignment Date

The date on which an eDiary device is assigned to a subject for the first time after completion of initial screening at week -4 visit.
 - eDiary Day

A day in which a subject uses the eDiary.
 - Information Day

A day which is either a headache day or an eDiary day.
 - Migraine Day

A migraine day is defined as any calendar day in which the subject experiences a qualified migraine headache (onset, continuation, or recurrence of the migraine headache). Please see exceptions in [Appendix 5.7](#). A qualified migraine headache ([IHS, 2013](#)) is defined as a migraine with or without aura, lasting for ≥ 30 minutes, and meeting at least one of the following criteria:

 1. ≥ 2 of the following pain features:
 - Unilateral
 - Throbbing
 - Moderate to severe
 - Exacerbated with exercise/physical activity
 2. ≥ 1 of the following associated symptoms:
 - Nausea and/or vomiting
 - Photophobia and phonophobia

If the subject took a migraine-specific medication (ie, triptan or ergotamine) during aura, or to treat a headache on a calendar day, then it will be counted as a migraine day regardless of the duration and pain features/associated symptoms.
 - Monthly Migraine Days

Number of migraine days between each analysis visit that are normalized in a 28-day interval. Monthly migraine days at baseline are the number of migraine days in the baseline period that are normalized in a 28-day interval. Days without eDiary data in each normalized monthly interval will be prorated. All details of calculation are in [Section 5.1.4](#) (The same proration method will be applied for other efficacy endpoints thereafter).

- Duration of Migraine

The duration of migraine in years (migraine with aura or migraine without aura, whichever is earlier) is calculated by the following formula: current age (in years) - age at migraine onset (in years).

Current age is calculated by the following formula, the date of informed consent – birth date (at least the year).

If the current age calculated as detailed above or the age at migraine onset is missing then duration of migraine will be missing.

- Achievement of at least a 50% reduction from baseline in monthly migraine days at month 12

Calculated based on the following: if (monthly migraine days in the last month of the treatment period - baseline monthly migraine days)*100/baseline monthly migraine days is less than or equal to - 50%

- Migraine Attack

An episode of any qualified migraine headache or migraine specific medication intakes for aura only. The following rules will be used to distinguish an attack of long duration from two attacks, or to distinguish between attacks and relapses:

a) A migraine attack that is interrupted by sleep, or temporarily remits, and then recurs within 48 hours will be considered as one attack and not two.

b) An attack treated successfully with medication but with relapse within 48 hours will be considered as one attack.

c) A migraine attack lasting more than 48 hours will be counted as one attack.

- Monthly Migraine Attacks

Number of migraine attacks between each analysis visit. Monthly migraine attacks at baseline are the number of migraine attacks in baseline period. Days without eDiary data are handled by proration according to [Section 5.1.4](#).

[figure not shown]
[figure not shown]
[figure not shown]
[figure not shown]
[figure not shown]
[figure not shown]
[figure not shown]
[figure not shown]
[figure not shown]
[figure not shown]
- Headache Day

A headache day is any calendar day in which the subject experiences a qualified migraine or non-migraine headache (initial onset, continuation or recurrence of the headache). A qualified headache is defined as:

[figure not shown]
- a qualified migraine headache (including an aura-only event that is treated with acute migraine-specific medication), or
- a qualified non-migraine headache, which is a headache that lasts ≥ 30 minutes and is not a qualified migraine headache, or
- a headache of any duration for which acute headache treatment is administered.

- Monthly Headache Days

Number of headache days between each analysis visit. Monthly headache days at baseline are the number of headache days in baseline period. Days without eDiary data in each monthly interval are handled by proration according to [Section 5.1.4](#).

- Response

At least 50%  reduction from baseline in monthly migraine days.

- Cumulative Monthly Migraine Days

Cumulative monthly migraine days during treatment period is the sum of qualified monthly migraine headache days during the entire treatment period normalized into the 28-day period. If eDiary compliance $\geq 50\%$ (definition in [Section 5.6](#)) then the cumulative monthly migraine days are calculated according to the formula:

$28 * (\text{Total number of observed eDiary migraine days} / \text{Number of information days during treatment period})$;

If eDiary compliance is $< 50\%$, it is set up to missing.

- Change from baseline

When change from baseline is of interest, the following formula will be used for each scheduled visit and time-point where baseline and post-baseline values are both available:

Change from baseline = post-baseline value – baseline value; and

Percent change from baseline = change from baseline *100/ baseline value

The change from baseline in monthly efficacy measurement is the monthly efficacy measurement in the monthly interval prior to the given time point minus the baseline monthly efficacy measurement. Please, refer to the monthly intervals for efficacy endpoints defined in [Table 2-3](#). For example, change from baseline in monthly migraine days in the last month (month 52) of the treatment period will be calculated based on the following:

[figure not shown]
(Monthly migraine days in the last month of the treatment period) – (monthly migraine days during the baseline phase)

If baseline or post-baseline values are missing, then the change from baseline will be missing.

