12.5 Analysis of secondary endpoints

12.5.1 Efficacy and/or Pharmacodynamic endpoint(s)

- Proportion of subjects completing the treatment period at month 12 on the initially assigned treatment

This variable will be analyzed same as that of the primary endpoint.

- Global satisfaction as measured by PGI at month 12 for subjects completing treatment period on initially assigned treatment

Patient will be considered as responder if PGI-I score is 5, 6, or 7. Proportion of responders based on PGI-I score at month 12 will be analyzed same as that of the primary endpoint.

- Cumulative average change from baseline on the monthly migraine days during the treatment period for subjects on the initially assigned treatment (month 1-12)

The average of monthly migraine days will be obtained cumulatively at each month across 12 months (e.g. at month 2 the average will be based on data from month 1 and 2; at month 3 the average will be based on month 1 to 3 and so on). The cumulative average change from baseline on the monthly migraine days will be derived using difference between cumulative average at each month and baseline monthly migraine days. The change from baseline will be analyzed using a linear mixed effects model including treatment group, baseline value, stratification factor(s), scheduled visit, and the interaction of treatment group with scheduled visit.

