2.7.2 Statistical hypothesis, model, and method of analysis

Analysis of above mentioned secondary endpoint will utilize the FAS.

- Proportion of subjects completing the study at Month 12 on the initially assigned treatment

The responders and non-responders for this endpoint are defined as given below:

Subjects who complete one year on the initially assigned treatment are considered as responders.

A subject will be considered as a non-responder if a subject do not complete one year on the initially assigned treatment. This includes (a) subjects who discontinue initially assigned treatment permanently (b) subjects who switched to oral prophylactics other than initially assigned treatment.

In subjects with episodic migraine, the proportion of subjects completing 12 months on initially assigned treatment will be compared between the AMG334 treatment group and oral prophylactics group, in terms of odds ratio. Thus, below hypothesis will be tested between initially assigned treatment groups:

Null hypothesis: Odds ratio =1 vs Alternative hypothesis: Odds ratio \neq 1.

A Cochran-Mantel-Haenszel (CMH) test stratified by number of prior prophylactic migraine medication failures (1 vs. 2) will be used under a 2-sided significance level of 0.05. The p-value of the test, and the estimated odds ratio between AMG334 and active comparator, as well as its 95% confidence interval, will also be reported.

- Cumulative average change from baseline on the monthly migraine days during the treatment period week 4 to week 52 (Months 1-12)

The average of monthly migraine days will be obtained cumulatively every 4 weeks across 52 weeks (e.g. at week 8 the average will be based on data from week 1 to week 8; at week 12 the average will be based on week 1 to week 12 and so on). The cumulative average change from baseline in monthly migraine days will be derived using difference between cumulative average of each month and baseline monthly migraine days.

The change from baseline will be analyzed using a linear mixed effects repeated measures model including treatment group, baseline value, stratification factor(s), scheduled visit, and the interaction of treatment group with scheduled visit. If applicable, in the repeated statement,

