5.1.4 Other imputations

5.1.4.1 eDiary data

The eDiary includes the following clinical outcome assessments:

- Incidence of headache (ie, migraine with or without aura or non-migraine headache)
- Time of onset of headache
- Time of resolution of headache
- Pain severity per headache

- Symptoms (eg, nausea, vomiting, photophobia, phonophobia)
- Presence of aura
- Use of acute medication during aura or to treat headache

as well as, patient-reported outcomes (PROs) measures.

Missing eDiary data in the calculation of monthly measurements about subjects' migraine and non-migraine headaches will be handled using the following method:

1. For monthly intervals with ≥ 14 days of eDiary days (including retrospective eDiary days) in each interval:

a) Monthly frequency measurements (including migraine days, headache days, migraine attacks, [REDACTED]) will be prorated to 28-day equivalents. Prorated result does not need to be rounded.

[REDACTED]

2. For monthly intervals with < 14 days of eDiary use (including retrospective eDiary days), all monthly measurement will be set as missing and will be handled as described in [Section 5.1.5.3](#).

Table 5-2 Rules for handling missing and incomplete eDiary data

Monthly Endpoint	Condition	Proration Method (does not need to be rounded)
Monthly frequency measurements (including migraine days, headache days, migraine attacks, hours of migraine headaches, [REDACTED] [REDACTED])	If diary days in entire baseline or interval post baseline ≥ 14 (including retrospective eDiary days), then do proration; Else monthly measurement is set to missing [diary days is a day with all headache related questions completed retrospectively or not]	Number of observed migraine days * 28/ Number of information days in interval [information day is a diary day or headache day]

Missing PROs scheduled to be collected at office visit at certain assessment will not be imputed.

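### The SAP defines cumulative monthly migraine days in two differing ways, and its imputation steps allow a Week 52-only model that does not test the 52-week average

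*SAP*

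**What the plan says.** **Main derivation.** SAP 2.7.2: "The average of monthly migraine days will be obtained cumulatively every 4 weeks across 52 weeks". Protocol 12.5.1 describes the same running mean: "at month 2 the average will be based on data from month 1 and 2". Baseline is subtracted, and the result enters a repeated-measures model in the FAS with visit and treatment-by-visit terms. SAP 2.7.3 rules out imputation of migraine days in this analysis. A monthly value needs at least 14 diary days; with fewer, SAP 5.1.4.1 says "all monthly measurement will be set as missing".

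**Second definition.** SAP 5.6 has an entry for cumulative monthly migraine days: "the sum of qualified monthly migraine headache days during the entire treatment period normalized into the 28-day period". The formula is 28 times the "Total number of observed eDiary migraine days" divided by the information days in the treatment period. If eDiary compliance is below 50%, "it is set up to missing". For compliance the entry points back to SAP 5.6, where the rule begins "Compliance to eDiary at each month is calculated as". Its denominator is 28 days, or the actual interval length if that is longer. No whole-period version is given.

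**Sensitivity analysis.** SAP 2.7.4 and Table 2-5 specify multiple imputation under MAR, followed by the repeated-measures model of the cumulative average. SAP 5.1.4.3 applies the imputation to primary and secondary endpoints. SAP 5.1.4.3.2 imputes a change value at each visit. For change in monthly migraine days it names a linear mixed model, then adds that, because imputed data have no gaps, one "can use a fixed effects model looking only at the avisitn=2052/week52 data".

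**The concern.** The two definitions differ in three ways.

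- **Weighting:** each valid month counts equally in 2.7.2; each information day counts equally in 5.6.
- **Missing data:** fewer than 14 diary days in a month, against compliance below 50%.
- **Structure:** one value per visit, against one value per subject.

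A programmer who took the 5.6 entry as the derivation of this endpoint could obtain other values and other analysed subjects. In an open-label trial that choice should not be left until data are in hand.

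The imputation text raises a separate problem. A sensitivity analysis should keep the target quantity and vary the missing-data assumption. A Week 52 model of monthly change alters the target, so agreement or disagreement with the main result would say little about how missing data affect the 52-week average.

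**Working it through.** The documents state no numerical result for this endpoint, so there is no figure to reproduce. The 591-subject calculation concerns the primary endpoint and does not enter here.

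**Inputs from the SAP.** 52/4 = 13 intervals of 28 days (364 days); 14-diary-day rule (5.1.4.1); 50% rule and pooled formula (5.6). The subjects below are constructed. I assume that the running mean uses the valid months only, which 2.7.2 does not say, and that information days equal diary days.

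**1. Complete diaries.** Three months with 8 migraine days, then ten with 4.
- 2.7.2 at Week 52: (3×8 + 10×4)/13 = 64/13 = 4.92.
- 5.6: 28×64/364 = 4.92. The two agree.

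**2. Half-complete diaries, same underlying rates.**
- 14 diary days (2 migraine days) in each of the last ten months. 2.7.2 prorates 2×28/14 = 4 per month, giving 4.92. 5.6 gives 28×(24+20)/(84+140) = 28×44/224 = 5.50.
- 14 diary days (4 migraine days) in each of the first three months instead. 2.7.2 gives 4.92. 5.6 gives 28×(12+40)/(42+280) = 28×52/322 = 4.52.

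**3. Just below the monthly threshold.** 13 diary days (2 migraine days) in each of the last ten months. 2.7.2 keeps three months: 8.00. 5.6 gives 28×44/(84+130) = 28×44/214 = 5.76, and keeps the subject if compliance is counted over 364 days (214/364 = 59%).

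**4. Who is analysed.** A subject whose diary stops after Week 12 contributes Weeks 4 to 12 under 2.7.2. Under 5.6 the outcome depends on the missing denominator.
- *Counted over 364 days:* compliance is 84/364 = 23%, so the subject is missing. With a constant leaving rate, full diaries until leaving, and 60–90% still keeping the diary at Week 52 (all assumed), the share below half the period is 1−√0.9 = 5% to 1−√0.6 = 23%.
- *Counted per month:* in an interval of 28 days or fewer, 50% is 14 entries, the same as the 5.1.4.1 threshold. In a 33-day interval 14 entries are 42%, so the rules part only there.

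**5. Illustrative simulation.** Assumptions: 394 and 197 subjects, 200 runs, baseline about 9 days, true effect -2 days before flooring at zero, on-treatment data only, and a fixed 364-day denominator. Each subject's 2.7.2 value is the simple mean of valid months; the repeated-measures model was not fitted. Complete diaries are used in the first row; in the others diary use falls from 95% to 60%.

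| Scenario | Difference, 2.7.2 | Difference, 5.6 | Controls analysed, 2.7.2 / 5.6 |
|---|---|---|---|
| Complete data | -1.84 | -1.84 | 100% / 100% |
| 20% erenumab and 80% control dropout, unrelated to outcome | -2.07 | -1.88 | 88% / 35% |
| The same base rates, dropout related to outcome | -1.94 | -0.95 | 86% / 35% |

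This shows that the two can diverge. It does not predict the trial.

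**6. What the imputation step estimates.** SAP 5.6 defines change in a monthly measure as the interval before the time point minus baseline. SAP 5.1.4.3.2 derives the Week 52 responders from the imputed monthly data. On that reading the imputed change is monthly, and no later step averages it. With an assumed linear treatment effect over the 13 months:
- growing from -0.5 to -1.5: average (-0.5-1.5)/2 = -1.0; Week 52 alone -1.5;
- waning from -1.8 to -0.8: average (-1.8-0.8)/2 = -1.3; Week 52 alone -0.8;
- flat: the two are numerically equal, though still different quantities.

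**The case against.** The strongest reply is that the plan already indicates which rule governs. The SAP introduction ties the analysis to protocol section 12, SAP section 4 declares no departure from it, and protocol 12.5.1 matches 2.7.2. The 5.6 entry carries a different name, may serve a redacted analysis, and yields one value per subject, so it cannot feed a model with visit terms. All of this stands. It makes 2.7.2 the natural reading, but no sentence says so, and the 5.6 entry has no visible use.

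On imputation, the Week 52 wording is permissive, the same sentence first names a mixed model, and Table 2-5 states the right one. The dataset parameter is not named either; if it were the cumulative one, its Week 52 value would be the full-period average. That also stands. The wording elsewhere nevertheless points to monthly change, and the option is open as written.

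A reader might infer that the SAP holds three incompatible derivations of the endpoint. It does not: the Week 52 text is a modelling step in a sensitivity analysis, and the hypothesis in SAP 5.5.2 is the 2.7.2 variable read at month 12. A reader might also infer that 5.6 drops early leavers. That needs a fixed 52-week compliance denominator, which the SAP does not state.

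**Conclusion.** The point holds in two parts.

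**Definitions.** SAP 2.7.2 and 5.6 define cumulative migraine days differently. They coincide at Week 52 with complete diaries in 28-day intervals. With incomplete diaries they can give different values (4.92 against 5.50 or 4.52 in the constructed subjects) or different analysed subjects. The 5–23% range and the simulation rest on assumed dropout and a fixed 52-week denominator. That the results must differ in this trial is not shown.

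**Sensitivity analysis.** Run in the permitted Week 52 form on monthly change, it estimates the last-month effect and does not test robustness of the 52-week average. The gap depends on the effect's time course: 0.5 days in either assumed example, none if the effect is flat.

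The consequence is limited. SAP 2.6 names no key secondary objective, SAP 2.7.2 reports nominal p-values for this endpoint, and the primary endpoint and sample size are untouched. The change should be made because it is cheap and removes an avoidable choice.

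**What to change.** 1. State in the SAP that 2.7.2 governs this secondary endpoint. Add one line on how the running mean treats a missing month.
2. Delete the 5.6 entry, or label it as a separate descriptive variable with its own compliance denominator.
3. In 5.1.4.3.2, name the imputed variable as monthly migraine days. After each imputation, compute the cumulative average through each visit, subtract baseline, fit the 2.7.2 repeated-measures model, and pool. Remove the Week 52-only option for this endpoint.

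The cost is SAP wording and the matching programming instructions. No new data, visits or subjects are needed.
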